1.1.1 Impact of Cigarette Smoking on Oncologic Treatment and Outcomes

Smoking is a significant risk factor for cancer, and smoking cessation efforts have been widely implemented among smokers as primary prevention of cancer development. In addition to its effects on carcinogenesis, smoking also impacts premalignant-to-malignant progression [2-8] and increases the risks for perioperative morbidity and mortality. Due to its effect on small vessels and oxygenation, smoking may also decrease the effectiveness of adjunctive treatments such as radiation and chemotherapy while at the same time increasing symptom burden. Smoking also increases the risk of secondary cancers [2-8]. Importantly, there has been an increasing body of evidence indicating that smoking can be a barrier to successful administration and completion of multimodality oncology treatments (including chemotherapy, radiotherapy, and surgery), and smoking can reduce both the quality of life (QOL) and long-term survival. Comparison of the 5-year survival of lung cancer between smokers and non-smokers has shown that only 33% of smokers survive 5 years compared to 70% of non-smokers [3-9].

Smoking causes temporary changes in the blood and tissue microenvironment (increased tissue CO₂ and decreased O₂ carrying capacity)[2] and in reparative cell functions, which can lead to delayed wound healing [2]. This can be responsible for prolonged recovery, which in turn, leads to an increase in the risks of hospital-acquired infections and other postoperative complications.^[2-4] Smokers with gastrointestinal malignancies have a higher risk than non-smokers for surgical site infections (OR 1.25; 95% CI, 1.09–1.44), combined pulmonary complications (OR 1.60; 95% CI, 1.38–1.87), and reoperations (OR 1.20; 95% CI, 1.03–1.39)[10]. Complications of oncologic surgery (Appendix 1) can contribute to delays in the initiation of and lower ability to tolerate adjuvant therapy, further contributing to poor long-term cancer outcomes [11]. However, cigarette smokers diagnosed with cancer have not been a focus of smoking cessation efforts [12]. Cancer-directed treatments generally receive the bulk of attention after a cancer diagnosis, and smokers diagnosed with cancer represent a missed opportunity in smoking cessation and prevention of second cancers or recurrence of cancer.

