1.1.2. Benefits of Smoking Cessation in Cancer Patients

Quitting smoking has beneficial health effects regardless of patient age.[13] Individuals who stop smoking significantly decrease their risk of lung cancer compared to current smokers.[7] For patients diagnosed with cancer, smoking cessation can improve cancer

treatment tolerance and effectiveness,[14, 15] overall survival,[13] prevention of second primary malignancy,[8, 16] and QOL.[17] Multimodal cancer therapy most often includes surgical procedures. Minimizing postoperative complications in oncology patients undergoing surgical procedures is of paramount importance both for minimizing treatment-related morbidities and for allowing a patient to go on to other components of the multimodal therapy. A reduction in complications has been observed within 4 weeks of smoking cessation.[18] Smoking cessation is beneficial at any time point relative to lung cancer surgery, but “current” smoking status at the time of surgery has been associated with a poor postoperative QOL.[19] A recent meta-analysis of 6 studies addressing smoking and surgical complications found that stopping smoking can reduce the relative risk of postoperative complications by 41% (95% CI, 15% to 59%; $P = 0.01$); each week of cessation prior to surgery increased this effect by 19%.[20] In addition, stopping smoking prior to chemotherapy and radiation therapy reduces the total symptom burden (sum of 12 symptoms scored on an 11-point Likert scale) of cancer treatment during treatment (smokers vs. nonsmokers: 46.3 vs. 41.2; $P < 0.05$) and at 6 months after treatment (27.7 vs. 21.9; $P < 0.05$).[21] Fewer than 10% of smokers actively seek treatment for tobacco dependence. Over 80% of providers in oncology practices provide brief smoking cessation counseling, but fewer than 30% ask about smoking in subsequent visits.[22] Barriers to smoking cessation among oncology patients include provider lack of confidence and patient lack of motivation.[22] Adjunctive use of a self-help guide for stopping smoking has been associated with improved motivation and has been found to be a predictor of long-term smoking cessation in oncology patients.[23, 24] Thus, effective methods for smoking cessation exist, but they have not been tested in the setting of a multicenter clinical trial targeting cigarette-smoking oncology patients who are scheduled for surgery.

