8.0 DOSE AND TREATMENT MODIFICATIONS, UNBLINDING

8.1 Ancillary therapy, concomitant medications, and supportive care

8.1.1 Patients should not receive any other agent which would be considered treatment for smoking which can impact the primary endpoint. This includes, any nicotine replacement products (patch, gum, nasal spray, inhaler), bupropion, naltrexone,

8.1.2 Adjuvant chemotherapy and radiation therapy with curative intent for patients enrolled to this study is permitted.

8.1.3 Patients should receive full supportive care while on this study. This includes blood product support, antibiotic treatment, and treatment of other newly diagnosed or concurrent medical conditions. All blood products and concomitant medications such as antidiarrheals, analgesics, and/or antiemetics received from the first day of study treatment administration until 30 days after the final dose will be recorded in the medical records.

8.1.4 Diarrhea management is per the discretion of the treating physician. Diarrhea could be managed conservatively with medications such as loperamide.

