13.3 Primary analysis

Surgical complication incidence rates at 24 weeks after surgery will be compared between the intervention vs. control groups using a Fisher's exact test.

Logistic regression models will supplement the univariate analysis, using complication incidence as the dependent variable and will include smoking status at the time of surgery as an independent variable and also adjust for age, gender, FTND, time between randomization and surgery, and presence of adjuvant chemotherapy and/or radiation therapy. A separate logistic model will be created including treatment arm instead of smoking status. We will also explore the collinear relationship between arm and smoking status to see whether they can be included together in the logistic models.

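### The supplementary logistic models for the primary endpoint adjust for untimed, post-surgical adjuvant therapy, which is not a baseline confounder and may be partly a result of the complications being modelled

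*Combined protocol and SAP*

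**What the plan says.** Section 13.3 has two layers. Complication rates at 24 weeks "will be compared between the intervention vs. control groups using a Fisher's exact test", with no covariates. Then "Logistic regression models will supplement the univariate analysis". The first of these models is described as "using complication incidence as the dependent variable and will include smoking status at the time of surgery as an independent variable". The covariates are age, gender, FTND, time from randomization to surgery, and "presence of adjuvant chemotherapy and/or radiation therapy". The section continues: "A separate logistic model will be created including treatment arm instead of smoking status". I read this as the same model with arm substituted and the other covariates kept. A model containing both arm and smoking status may follow if collinearity allows.

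No text limits the adjuvant covariate to therapy planned before surgery, to therapy begun before a complication, or to any time window. Section 8.1.2 says "Adjuvant chemotherapy and radiation therapy with curative intent for patients enrolled to this study is permitted", so it is allowed and neither assigned nor restricted. The endpoint (13.2.1) runs to 24 weeks after surgery and includes 30-day death.

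The background describes how adjuvant therapy relates to outcome and exposure. Section 1.1.1 says that complications of oncologic surgery "can contribute to delays in the initiation of and lower ability to tolerate adjuvant therapy", and also describes smoking as an obstacle to giving and completing multimodality treatment, including chemotherapy and radiotherapy. Section 1.1.2 says that keeping complications low matters for "allowing a patient to go on to other components of the multimodal therapy", and that cessation can improve tolerance of cancer treatment.

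**The concern.** A covariate in a supporting model for a randomized comparison should normally be fixed before treatment could affect it. This one is determined after surgery, over the same weeks as the outcome. On the protocol's own account a complication can postpone or prevent adjuvant therapy, and a patient who dies within 30 days counts as a complication and has little chance of receiving any. Therapy may also come first and contribute to a later event. A single yes/no indicator cannot separate the two.

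At stake is how the supporting models are read. If receipt is also linked to arm or smoking by a route other than complications, conditioning on it biases the arm and smoking odds ratios. The models could then disagree with the Fisher test for a structural reason. In any case the adjuvant coefficient would look protective without therapy having any such effect. Section 13.4 reuses the primary approach for the expanded complication rate, so the covariate carries over there.

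**Working it through.** **1. The plan's own figures (13.6).** Rates 30% and 20%, two-sided 5%, 80% power.

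- Uncorrected: n = [1.96·√(2·0.25·0.75) + 0.8416·√(0.21 + 0.16)]² / 0.10² = (1.200 + 0.512)² / 0.01 ≈ 293.2, so 294 per arm.
- With continuity correction: (293.2/4)·[1 + √(1 + 4/(293.2·0.10))]² ≈ 312.8, so 313 per arm, or 626.
- Exact Fisher power at 313 per arm, by enumeration: 80.2%.
- Enrolment: 626/0.80 = 782.5, so 783.

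The plan's figures reproduce. They belong to the unadjusted test and do not involve the covariate.

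**2. Unadjusted arm term in a logistic model.** Expected cells are 93.9/219.1 (control) and 62.6/250.4 (varenicline). OR = (0.20/0.80)/(0.30/0.70) = 0.583. SE of log OR = √(1/93.9 + 1/219.1 + 1/62.6 + 1/250.4) = 0.1876. |z| = 0.539/0.1876 = 2.87. Power = Φ(2.87 − 1.96) ≈ 82%.

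**3. What conditioning on receipt does.** Let r(T,Y) be the probability of adjuvant therapy in arm T (1 = varenicline, 0 = placebo) with complication status Y. By Bayes' rule, among recipients

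OR(arm) = 0.583 × [r(1,1)/r(1,0)] / [r(0,1)/r(0,0)],

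and among non-recipients the same with 1 − r. If r does not depend on arm, the factor is 1 in both strata and the arm OR is unchanged. The adjuvant coefficient then simply returns the reverse effect: for receipt of 50% without and 25% with a complication, OR = (0.25/0.75)/(0.50/0.50) = 0.33; for 50% and 10%, 0.11.

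If r depends on arm as well, the factor is not 1. For a 5-point gap (52.5%/27.5% on varenicline, 47.5%/22.5% on placebo):

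- recipients: (0.275/0.525)/(0.225/0.475) = 1.106, OR 0.645;
- non-recipients: (0.725/0.475)/(0.775/0.525) = 1.034, OR 0.603;
- fitted common OR: 0.615.

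**4. Results.** Logistic fits to expected cell counts, 313 per arm, with approximate Wald power. All receipt rates are assumptions, because the documents give none. The simulated setting gives adjuvant therapy no effect on complications. Receipt is shown as without/with a complication.

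| Receipt, varenicline; placebo | Adjusted arm OR (true 0.583) | Power of arm term | Adjusted OR if true OR is 1 | Null rejection |
|---|---|---|---|---|
| 50/25; 50/25 | 0.583 | 80% | 1.00 | 5.0% |
| 50/10; 50/10 (extreme) | 0.583 | 77% | 1.00 | 5.0% |
| 51.5/26.5; 48.5/23.5 (3-point gap) | 0.602 | 75% | 1.03 | 5.4% |
| 52.5/27.5; 47.5/22.5 (5-point gap) | 0.615 | 71% | 1.06 | 6.0% |
| 55/35; 45/20 (10- and 15-point gaps) | 0.651 | 61% | 1.12 | 9.5% |

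A pattern of 50/35 against 40/20 gives OR 0.64 and power 66%. It weakens the complication effect but keeps the 10- and 15-point arm gaps, so it is not a milder case on the input that drives the bias. In all the patterns with a gap, the arm OR moves upwards, against varenicline.

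**5. What was not computed.** Every fit above is for the arm model. The smoking-status model has the same structure, and 1.1.1 links smoking directly to treatment delivery, but no size was derived for it.

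**The case against.** The strongest reply is that nothing decisive rests on these models. The Fisher test is primary and unadjusted, and no power or alpha is planned for the logistic arm term. That stands: the power and rejection figures above describe a supporting term, not the trial.

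Second, the mechanism that the documents state most clearly, complications affecting adjuvant therapy, does not by itself bias the arm OR. That stands too. A reader might infer that adjusting for a consequence of the outcome must distort the arm effect; step 3 shows that it need not. Bias needs a separate route from arm to receipt. The documents make one plausible, through cessation and treatment tolerance, but do not say who will receive therapy. The trial is double-blind, so arm can act only through the patient's condition. If varenicline raised abstinence by 20 points (an assumption), a 3–5 point gap would need receipt 15–25 points higher in quitters (3/0.20 and 5/0.20), and a 10–15 point gap would need 50–75 points. The large-gap row is therefore an upper illustration.

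Third, a reader might call the covariate purely a consequence of the outcome. The documents do not support that. Section 1.1.1 speaks of delay and reduced tolerance, so delayed therapy may still be recorded as present, and therapy could precede a late event. The defensible description is an untimed variable that mixes both directions.

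**Conclusion.** The concern holds at a modest size. Both 13.3 models include a post-surgical, undated covariate that the protocol's own background ties to complications and to smoking, and that is not a baseline confounder of either effect. With receipt depending on complications alone, the loss is about 2 points of power (5 in the extreme case) and a coefficient that should not be interpreted. With small arm gaps in receipt, the arm OR drifts from 0.58 to 0.60–0.62 and null rejection reaches about 6% at 5 points. With gaps of 10–15 points it reaches 0.65 and about 9.5%. All of this rests on assumed receipt rates and on therapy not causing complications. It would be wrong to infer that the primary result, the sample size of 626 or the type I error of the trial is compromised. The structural point does not depend on the assumed rates; the sizes do.

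**What to change.** Delete the adjuvant-therapy covariate from both 13.3 models, from any model combining arm and smoking status, and from the expanded-complication models under 13.4. Keep age, gender and FTND. This point makes no claim about the time from randomization to surgery, which can stay as listed.

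Report adjuvant therapy descriptively by arm, with its start date relative to the first complication where available. If an adjuvant-adjusted model is still wanted, label it exploratory and count only therapy begun before the event.

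The cost is one phrase removed, one descriptive table added, and an adjuvant start date if it is not already captured. The downside is that late events caused by adjuvant therapy itself would no longer be adjusted for. The primary test and sample size do not change.

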13.4 Additional Analyses

We will compare changes from baseline in patient quality of life related domains (LASA-12, PHQ-9, SEQ12) between the intervention and control groups using analysis of covariance and linear mixed model repeated measures analysis for each assessment domain. Specifically, we will analyze each LASA domain with a separate ANCOVA model using the change from baseline to 12 weeks post-surgery as the dependent variable, followed by a similar analysis using the change from baseline to 24 weeks post-surgery. Each LASA question corresponds to a separate domain. For the PHQ-9 and SEQ12, we will use the scale scores in a repeated measures analysis involving data from all time points (baseline, 6, 12, and 24 weeks). For the PHQ-9 there is one overall score and for the SEQ12 there are two scales (internal stimuli and external stimuli).

The WIWI survey will be analyzed by comparing the proportion of patients at the end of the treatment period (i.e., 12 weeks after surgery) and at 24 weeks after surgery who endorse each treatment (intervention versus control) via Fisher's exact testing.

These QOL-related domain variables will be included in the modeling process of the primary and other secondary analyses as potentially concomitant confounding covariates so as to produce more efficient estimates from the models. Sensitivity analysis for potential differences between groups demonstrated via the ANCOVA and repeated measures models will be assessed using Generalized Estimating Equations models to account for the correlation of repeated measures on the same patient.

We will compare post-operative care (length of hospital and high dependency unit stay) between the intervention vs. control groups using separate logrank testing of Kaplan-Meier estimates for length of hospital stay and length of high dependency unit stay and supplemented by Cox models to control for concomitant covariates. The assumptions underlying the Cox model will be tested for veracity.

For the expanded complication rate, we will utilize the same analysis approach as the primary endpoint analysis for all complications listed in Appendix I. We will also compare the incidence rates of each specific type of complication between arms.

We will also measure treatment adherence. The number of study visits completed by each patient during the treatment phase will be summarized and compared between groups using the rank

sum test. Patient self-report will be used to collect adherence data on the use of the quitline and the medication adherence for the patients receiving the multi-faceted smoking cessation intervention. To assess medication compliance, patients will report to the study staff at each visit the amount of study medication used each day. In addition, patients will return unused medication at each study visit and study staff will maintain drug accountability logs to account for dispensed and returned medication. The amount of study medication taken by each patient will be calculated weekly. Adherence data on teachable moment delivery from the surgical team will be collected by the study staff at the time of the message delivery. These data will be summarized using simple descriptive statistics to indicate the degree of treatment adherence that is achieved for the multi-faceted smoking cessation intervention.

Rates of smoking abstinence will be compared between arms using Fisher's exact test and logistic regression models. Abstinence definitions are based upon the Society for Research on Nicotine and Tobacco (SRNT) Working Group recommendations.[88] The major advantage of point prevalence estimates is that they are widely reported in the literature and can be verified biochemically. However, point prevalence abstinence does not account for slips/lapses that might occur between follow-up periods. Prolonged abstinence is defined as smoking abstinence sustained after an initial 2-week grace period[88] and accounts for initial lapses. However, prolonged abstinence cannot be verified biochemically short of daily biochemical confirmations and, ultimately, must rely on self-report. Research suggests that self-reports among smokers in general tend to be accurate, and misreporting rates are generally very low.[89] We allow for a 2-week grace period after TQD based upon the SRNT Working Group recommendations.[88] Prolonged smoking abstinence will be adjudicated if the following criteria are met: 1) Self-reported smoking abstinence since 2 weeks after the TQD. This will be identified by a negative response to the question, "Since xx/xx/xxxx, which was 2 weeks after your TQD, have you smoked any tobacco, even a puff, for 7 consecutive days or at least once each week on 2 consecutive weeks?" and 2) No failed biochemical confirmation of self-reported smoking abstinence at any previous outcome assessment. Point prevalence smoking abstinence will be adjudicated if both of these criteria are met: 1) Self-reported smoking abstinence for the last 7 days. This will be identified by a negative response to the question, "Have you smoked any tobacco, even a puff, in the past 7 days?", and 2) Salivary cotinine less than 15 ng/mL. Relapse will be defined as smoking on 7 consecutive days or smoking at least once each week on 2 consecutive weeks.[88]

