1.3 Study Overview

This will be a randomized clinical trial. The primary goal is to assess the effect of smoking cessation treatment on surgical complications. We will also report the impact of alternative treatments on QOL and post-operative care. According to the US Guidelines[1], although counseling and medication are effective when used alone, the combination of both is more effective than either alone. Thus clinicians should encourage smokers who want to quit, to use both counseling and medication in trying to quit smoking (#7 of the 10 key guideline recommendations). In this study, 626 cancer surgery patients will be randomized 1:1 to a "protocolized" smoking cessation program (varenicline plus a brief no-smoking message from the surgical team and behavioral support provided by a telephone smoking quitline [NCI's [name]]), or to placebo plus a brief no-smoking message from the surgical team and behavioral support provided by the telephone smoking quitline). Surgery must occur after the target quit date (TQD) defined at baseline and can be performed no sooner than 10 days after randomization and no more than twelve weeks after randomization. The study will remain open to accrual until 626 patients have had surgery and are followed for 24 weeks after surgery for surgical complications. The primary outcome will be the rate of surgical complications, as identified from an investigation of the American College of Surgeons-National Surgical Quality Improvement Program (ACS-NSQIP). Secondary outcomes include QOL, post-operative care (length of hospital and high dependency unit stay), and rates of smoking abstinence. All study participants will have the option of enrolling in the correlative genetic study. This correlative study will look at important genetic variants in nicotinic receptor gene cluster (*CHRNA5-CHRNA3-CHRNA4*) and nicotine metabolism (*CYP2A6*) that have been shown to impact successful smoking abstinence. This will include a blood draw at baseline, and tobacco use outcome will be determined by salivary cotinine at baseline and every six weeks after surgery for 12 weeks, with a final measurement at 24 weeks.

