5.0 STUDY CALENDAR

Pre-Study Testing Intervals

- To be completed \leq 16 DAYS before registration: History and physical.
- To be completed \leq 6 months before registration: Serum creatinine.

Visit week	Prior to Surgery		Day of Surgery**	Post-Surgery***			
	Prior to Registration†	Baseline*	0	6	12	18	24
Visit #	1	2		3 (A)	4 (A, B)	5 (A, B)	6
Tests and observations							
History & physical (weight, bp, pulse)	E	E		X			X
Height	X						
Serum creatinine	X						
Pregnancy test	C						
Concomitant therapies		X		X	X	X	X
Adverse events		X		X	X	X	X
Surgical adverse events				X(1)	X(1)	X(1)	X(1)
Suicidal ideation monitoring				X (2)	X (2)	X (2)	X (2)
Tobacco use assessment (Appdx IX)	X	X	X	X	X	X	X
Surgical team message		X					
NCI Smoking Quitline		X (3)		X (3)	X (3)		
Sample submission							
Salivary Cotinine Measure		X	X	X	D	D	X
Patient questionnaires							
Contemplation Ladder (Apdx III)	X			X	X		X
SEQ-12 (Apdx IV)		X		X	X		X
FTND (Apdx V)		X					
PHQ-9 (Apdx VI)	X (4)			X	X		X
LASA-12 (Apdx VII)		X			X		X
Was It Worth It Survey (Apdx VIII)					X		X
Drug and Behavioral Support Adherence Logs (Apdx X)		X		X	X		
Correlative study (optional)							
Whole blood	To be collected at baseline, see Sections 6.2 and 14.0.						

† Pre-study testing may be performed on the same day as the baseline visit (see also, Section 7.1).

* Baseline: After randomization and at the time the surgical message is discussed with the cancer patient. If performed within 7 days prior to baseline, the Tobacco Use Assessment need not be repeated.

** Surgery must occur after the TQD defined at baseline and can be performed no sooner than 10 days after randomization and no more than twelve weeks after randomization.

*** Post surgery visits can be +/- 14 days

A Patient-completed booklets for Weeks 12 and 18 should be given to patients at the Week 6 visit. Institutional staff should telephone patients within one week prior to Weeks 12 and 18 to remind them that they will either be completing these booklets by telephone at Weeks 12 and 18 or that they may bring the completed booklet to the clinic when they provide saliva samples for cotinine measurements (see Footnote D).

B May be done by telephone or in person (see footnote D).

C For women of childbearing potential. Must be done within 7 days prior to registration/randomization.

D Patients will be asked to come to the treating institution to provide saliva samples for cotinine measurement. A physician visit is not required.

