13.5 Correlative and companion substudy analyses

13.5.1 Correlative substudy analysis (A211401)

Salivary cotinine is an evidence-based biochemical method to confirm tobacco use that significantly increases the accurate identification of current smoking. Data demonstrate that 30-40% of cancer patients who smoke do not accurately report smoking status even using structured assessments (97-98). As a result, quantitative cotinine analyses (96) will be used to increase the accuracy of identifying current smoking, which will in parallel be used to evaluate changes in study outcomes using a more accurate methodology. For this study, a cutoff of 15 ng/mL will be used to define biochemically confirmed current smoking (>15) according to recommendations from the Society for Nicotine and Tobacco Research (95).

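### The prolonged-abstinence rule in 13.4 overlooks a failed cotinine check at the visit being scored, so a first failure at week 24 never counts

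*Combined protocol and SAP*

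**What the plan says.** Section 13.4 of the combined protocol and SAP gives two definitions of abstinence.

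- **Prolonged abstinence** has two criteria. The first is "Self-reported smoking abstinence since 2 weeks after the TQD", taken from a question about use on seven consecutive days or at least weekly in two consecutive weeks. The second is "No failed biochemical confirmation of self-reported smoking abstinence at any previous outcome assessment".
- **Point prevalence** needs a negative seven-day self-report and "Salivary cotinine less than 15 ng/mL".

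The section explains its reliance on self-report by saying that "prolonged abstinence cannot be verified biochemically short of daily biochemical confirmations and, ultimately, must rely on self-report", and adds that, among smokers in general, "misreporting rates are generally very low". Section 13.5.1, writing about this trial's kind of patient, says: "Data demonstrate that 30-40% of cancer patients who smoke do not accurately report smoking status even using structured assessments". Section 14.1.1 repeats the 30-40% figure.

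Saliva is required of every patient. Section 6.2 and the calendar in 5.0 schedule it at baseline, surgery and weeks 6, 12, 18 and 24. Section 1.3 describes collection "every six weeks after surgery for 12 weeks, with a final measurement at 24 weeks". Section 13.2.2 lists abstinence as a secondary endpoint measured by both self-report and cotinine.

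**The concern.** The second criterion looks backwards only. A patient can deny smoking at a visit, give a saliva sample at that visit which shows otherwise, and still be scored prolonged-abstinent there, provided no earlier sample failed. At weeks 6, 12 and 18 the next visit corrects this. At week 24 there is no next visit, so the last mandatory sample cannot affect this endpoint at all. The same patient, on the same sample, fails point prevalence.

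At stake is the between-arm comparison of prolonged abstinence by Fisher's exact test and logistic regression. False claims let through in both arms raise both rates. If the misreporting probability is the same in each arm, they also pull the difference towards zero.

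**Working it through.** The plan states no expected abstinence rate, so there is no figure of its own to reproduce. The check has two parts: applying the rule to failure patterns, and bounding its effect.

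**1. The rule applied visit by visit.** Assume that criterion 1 is met by self-report throughout, all samples are present, and the outcome assessments are weeks 6, 12, 18 and 24. *Yes* means scored prolonged-abstinent. The amended rule counts failures up to and including the scored visit.

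| First failed confirmation | Rule | Wk 6 | Wk 12 | Wk 18 | Wk 24 |
|---|---|---|---|---|---|
| Week 6 | as written | yes | no | no | no |
| | amended | no | no | no | no |
| Week 12 | as written | yes | yes | no | no |
| | amended | yes | no | no | no |
| Week 18 | as written | yes | yes | yes | no |
| | amended | yes | yes | no | no |
| Week 24 | as written | yes | yes | yes | yes |
| | amended | yes | yes | yes | no |
| None | both | yes | yes | yes | yes |

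The rules differ only at the visit of first failure. For weeks 6 to 18 the error lasts one visit. For week 24 it is permanent.

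**2. A bound on the effect.** Let *a* be the true prolonged-abstinence rate in an arm, *m* the probability that a non-abstainer claims abstinence, and *f* the share of those false claimants with no earlier failed sample. Assume that true abstainers test below 15 ng/mL. Then

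scored rate = a + m·f·(1 − a).

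With the same *m* and *f* in both arms, the arm difference is multiplied by (1 − m·f).

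Inputs:
- *m* = 0.30 to 0.40, from 13.5.1. This is a stand-in, because that figure concerns misreporting of smoking status, not the criterion 1 question.
- *a* = 0.40 versus 0.25: assumed, not in the documents.
- *f*: not in the documents, shown from 0.1 to 1.

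| f | Factor, m = 0.30 | 15-point difference becomes | Factor, m = 0.40 | 15-point difference becomes |
|---|---|---|---|---|
| 1.0 | 0.70 | 10.5 (58% vs 47.5%) | 0.60 | 9.0 (64% vs 55%) |
| 0.5 | 0.85 | 12.75 | 0.80 | 12.0 |
| 0.1 | 0.97 | 14.55 | 0.96 | 14.4 |

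The row *f* = 1 is the ceiling. It fits the first scored visit, or patients whose earlier samples are all missing.

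In patients, for one arm of 313 (Section 13.6) at week 24, the excess counted as abstinent is 313·m·f·(1 − a). Over *a* = 0.20 to 0.40, it runs from 313 × 0.30 × 0.1 × 0.60 = 5.6 to 313 × 0.40 × 1 × 0.80 = 100.2. A range of about 6 to 100 shows that the week-24 size is undetermined; it is not an estimate.

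**The case against.** **Prolonged abstinence cannot be verified by spot samples.** The plan says so, and it is true that one cotinine value cannot establish abstinence over months. That is a reason not to treat a negative sample as proof. It does not explain why a failed sample disqualifies at an earlier visit but not at the current one.

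**Criterion 1 tolerates isolated lapses.** A patient can answer it truthfully and still have positive saliva. This stands: a positive sample does not by itself show that the answer was false. But the rule already disqualifies such patients at every earlier visit, so exempting only the scored visit is inconsistent.

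**Previous may have been meant to include the current visit.** Possibly, but nothing in the documents says so. If it was, the change merely records the intent.

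**The sample is used elsewhere.** This also stands. Point prevalence applies the cotinine limit, and 13.5.1, 14.1.2 and 14.1.3 plan parallel analyses with biochemically confirmed tobacco use and an assessment of self-report accuracy. These limit the harm but leave the prolonged-abstinence rule unchanged.

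**Most persistent deniers would be caught before week 24.** With complete sampling they would fail at week 6, 12 or 18, and patients who admit sustained smoking should fail criterion 1. What remains at week 24 is mainly late relapse with denial, plus patients with missing earlier samples. This is why the *f* = 1 figures are a ceiling.

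**Cessation is not the trial's focus.** Section 2.0 says so, and 2.2.6 compares abstinence only as a covariate of the primary outcome. This bears on priority, not on whether the rule classifies correctly.

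**Conclusion.** The gap is real. As written, a failed confirmation at the scored visit does not count towards prolonged abstinence, and a first failure at week 24 never counts. Overstatement of the rates follows if some non-abstainers claim abstinence. Attenuation of the arm difference further requires equal misreporting in the two arms; unequal misreporting could move the difference either way. The attenuation factor is bounded below by one minus the misreporting rate among non-abstainers with no earlier failed sample. Its value at week 24 cannot be obtained from the documents.

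The reach is one of two secondary abstinence definitions. The Fisher comparison of complications does not use it, and the supporting logistic model uses smoking status at surgery.

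A reader might infer more, but the documents do not support it:

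- *That the week-24 difference shrinks by 30-40%.* That needs *f* = 1, equal misreporting, and a status-misreporting figure applied to a different question.
- *That the genetic substudy inherits the error.* Section 13.5.2 bases abstinence on the tobacco use assessment and cotinine and does not name prolonged abstinence.
- *That 13.4 and 13.5.1 contradict each other on misreporting.* One concerns smokers in general, the other cancer patients who smoke. The fair criticism is that the general statement is poor support for relying on self-report in this population.
- *That missing saliva must be scored as unconfirmed.* The rule does let a missing sample pass, and weeks 12 and 18 may be telephone contacts with saliva given separately. How to score such visits is a debatable choice, and closing this gap does not depend on it.

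**What to change.** In 13.4, insert *the current or* before *any previous* in the second prolonged-abstinence criterion, so that a failed confirmation at the scored visit disqualifies in the same way as an earlier one. Optionally, report the self-report-only version as a sensitivity analysis. Beside the statement that misreporting is very low, note that it concerns smokers in general and that 13.5.1 and 14.1.1 give 30-40% for cancer patients.

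The cost is a few words. No visit or sample is added, since saliva is already mandatory. Reported prolonged-abstinence rates will be slightly lower, and a few patients with a permitted isolated lapse near the scored visit may be disqualified, as the rule already does at earlier visits.
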